#### **6.3.4. Safety Analysis Set**

The Safety Analysis Set includes all patients who are randomized and have taken at least 1 dose of randomized therapy. Safety analyses will be based upon randomized treatment. The Safety Analysis Set will be the primary population used for safety analyses.

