#### **12.3.4. Safety Analysis Set**

All patients who are randomized and take at least 1 dose of randomized therapy will be included in the Safety Analysis Set. Safety analyses will be based on randomized therapy.

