## **12.8. Safety Evaluation**

Descriptive statistics will be used to summarize the safety data by randomized treatment group for the double-blind period. All safety evaluations will be conducted based on the Safety Analysis Set. Observed data will be listed by patient.

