#### 4.4. Randomization

Randomization will be carried out using an interactive response technology (IRT) system, with central randomization following a 1:1 ratio between the 2 treatment arms, based on a permuted-block randomization method. Randomization will be stratified by the following factors:

- eGFR value at Screening (30 to <60 mL/min/1.73 m^2 and ≥60 mL/min/1.73 m^2)
- Urine protein excretion at Screening (≤1.75 g/day and >1.75 g/day)

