### **6.3. Analysis Populations**

#### **6.3.1. Full Analysis Set**

The Full Analysis Set (FAS) includes all patients who are randomized and take at least 1 dose of randomized therapy. Patients in the FAS will be analyzed according to randomized treatment assignment. If a patient is incorrectly stratified (ie, randomized according to an incorrect stratification), the patient will be analyzed under the randomized treatment for the stratum recorded in the IRT. All efficacy analyses for the double-blind period will be based on the FAS at the time of final analysis.

If a total of at least 10% of randomized patients did not receive any dose of randomized therapy, analysis of the primary and key secondary endpoints will be repeated based on all randomized patients as a sensitivity analysis.

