### **7.3. Protocol Deviations**

Protocol deviations for missed visits, missed assessments, out-of-window visits or assessments, and violations of inclusion/exclusion criteria (where possible) will be determined based on available data. All other protocol deviations will be collected by the clinical research associates.

Protocol deviations that could potentially affect the efficacy or safety conclusions of the study will be identified, and the assessment of determination of evaluable patients for analysis populations (PPPA, PPFA and PK Analysis Set) will be performed and approved by the Study Statistician, Medical Monitor, and Clinical Study Manager prior to database lock and unblinding of individual patient treatment information.

Evaluability of patients will be based on the following:

- Compliance of study entry criteria (inclusion and exclusion)
- Correct stratification at randomization
- Received the randomized treatment
- Adequate study medication exposure (no extended dosing interruptions)
- Adequate treatment compliance based on prescribed dose level (within 80% to 120%)
- No prohibited concomitant medications or therapies during the study
- No accidental or intentional unblinding at the investigational site

- No other major protocol deviations that may affect efficacy or safety conclusions, may include the following:
  - Non-withdrawal although at least 1 withdrawal criterion was met
  - Extensive visit window violations
  - Extensive missing visits
  - Nonadherence to study procedures
  - Inadequate handling of study medication

Major protocol deviations will be summarized by deviation category (overall and due to coronavirus disease 2019 [COVID-19]) and presented in a by-patient data listing.

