### **10.1.3. On-Treatment Summaries**

Select summaries for TEAEs while on-treatment will additionally be prepared. On-treatment will be defined as TEAEs starting  $\leq 30$  days from date of last dose in randomized treatment period for patients who discontinue treatment or any TEAE prior to first dose in OLE for patients who complete the randomized treatment period. Summaries will be prepared for TEAEs associated with safety topics of interest in Section 10.1.2. Patient incidence of on-treatment TEAEs and the total number of entries by PT will also be provided.

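### Safety is grouped by randomized treatment with no rule for a patient who takes the other blinded drug, so events on that drug are misattributed or possibly left out

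*SAP*

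**What the plan says.** SAP 6.3.4 sets the membership of the safety population: "The Safety Analysis Set includes all patients who are randomized and have taken at least 1 dose of randomized therapy". It then sets the grouping: "Safety analyses will be based upon randomized treatment". Protocol 12.3.4 agrees: "Safety analyses will be based on randomized therapy". So does Protocol 12.8: "Descriptive statistics will be used to summarize the safety data by randomized treatment group for the double-blind period". The protocol synopsis repeats both.

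The Full Analysis Set has the same membership rule in SAP 6.3.1, "The Full Analysis Set (FAS) includes all patients who are randomized and take at least 1 dose of randomized therapy", and is also analysed as randomized. The two sets therefore hold the same patients in the same columns.

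SAP 7.3 lists "Received the randomized treatment" among the evaluability criteria. These decide membership of the two per-protocol sets and the pharmacokinetic set, not of the Safety Analysis Set.

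The on-treatment adverse event summaries in SAP 10.1.3 ("On-treatment will be defined as TEAEs starting" within a stated number of days of the last dose) select events by timing, not by which drug was being taken.

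Neither document contains an as-treated rule, an actual-treatment variable, or a supplementary safety analysis by drug received.

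**The concern.** The safety objective is to describe what sparsentan does to the patients who take it. Where assignment and exposure differ, grouping by assignment answers a different question.

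Both drugs are over-encapsulated in the same size of blinded capsule, and the schedules show 13 dispensing visits per patient, so a kit error is possible. The evaluability criterion in SAP 7.3 can remove a wrongly dosed patient from the per-protocol efficacy analyses. Nothing comparable exists for safety. SAP 6.3.1 also plans a sensitivity analysis for the case where 10% or more of randomized patients are never dosed, but nothing for patients dosed with the wrong drug.

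At stake is a modest dilution of between-arm differences for common events. For a rare event, one case could stand in the wrong column or in none. Liver events are the obvious example: SAP 10.1, 10.1.1 and 10.4.3 tabulate, time and plot them by treatment group.

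**Working it through.** The plan gives no figure on this point to reproduce. The check is a reading of the text, followed by arithmetic for scale.

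**Inputs**
- Planned size: about 380 (SAP 4.1).
- Allocation: "central randomization following a 1:1 ratio between the 2 treatment arms" (SAP 4.4), so n = 380/2 = 190 per arm.
- Dispensing visits: 7 in Protocol Table 15.1-1 (Day 1, Weeks 2, 4, 6, 12, 24, 36) and 6 in Table 15.1-2 (Weeks 48, 58, 70, 82, 94, 106), so 13 per patient and at most 13 × 380 = 4,940 in all.
- Misdispensing rate: not given. The number of affected patients, m, is an assumption, shown from 1 to 19.
- Event risks: assumed, for illustration only, at 10% on sparsentan (pS) and 2% on irbesartan (pI).

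**Step 1. What the rule does to each kind of patient**
- Took only the assigned drug: no effect.
- Took both drugs: in the set, with all events under the assigned arm. Only events that arose on the other drug are misattributed.
- Took only the other drug: depends on what randomized therapy means, which is not defined. If it means the assigned drug, the patient is outside the set and the events are left out. If it means any double-blind drug, all the events are counted under the drug not taken.

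The per-protocol sets are subsets of the Full Analysis Set, so a further criterion of having received the randomized treatment adds more under the second meaning. That favours the second meaning but does not settle it, because under the first the criterion could still remove patients who took both drugs.

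**Step 2. Ceiling for one patient**

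1/190 = 0.0053, or 0.53 percentage points in an arm's incidence. This is a maximum. It is reached only when the column in which the patient is placed decides whether that arm shows the event.

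**Step 3. Expected dilution**

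If m of n patients in one arm take the other drug throughout and are counted as randomized, the expected risk difference is (pS - pI)(1 - m/n). If m patients in each arm do so, it is (pS - pI)(1 - 2m/n). Grouping by drug received gives pS - pI = 8.0 points.

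| m | One arm affected: 8.0 × (1 - m/190) | m in each arm: 8.0 × (1 - 2m/190) |
|---|---|---|
| 1 | 7.96 | 7.92 |
| 5 | 7.79 | 7.58 |
| 10 | 7.58 | 7.16 |
| 19 | 7.20 | 6.40 |

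At m = 1 the loss is about 0.5% to 1% of the difference. At m = 19 it is 10% to 20%, but that would mean one patient in ten on the wrong drug.

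**Step 4. Rare events**

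Assume 2 liver cases per arm and misdispensing in 0.5% to 2% of patients, independent of the event. The expected number of misplaced cases is 2 × 0.005 = 0.01 to 2 × 0.02 = 0.04 per arm. A misplaced case is unlikely. If one occurs, it can turn 1 versus 0 into 0 versus 1.

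**The case against.** The protocol and SAP agree with each other, so there is no contradiction. Grouping as randomized preserves the randomized comparison. The plan also has controls: central allocation through the interactive system, bottles labelled with a medication identification number (Protocol 8.2.1), and accountability at visits. Rare serious events do not rest on grouped tables alone. Liver abnormalities are reported individually within 24 hours (Protocol 10.3.1), the monitoring committee reads narratives and may ask for unblinded patient data (Protocol 13.2), and plasma is assayed for both drugs at several visits. All of this stands, and it keeps the point small. None of it regroups a table or says where a wrongly dosed patient belongs.

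A reader might infer three stronger things that the documents do not support:

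- That the SAP expects wrong dispensing. Receipt of the randomized treatment is one line in an evaluability checklist. It shows that departures were thought of, not that they are expected, and no rate is given.
- That every adverse event in a wrongly dispensed patient is charged to the other drug. For mixed exposure this holds only for events on the wrong drug. For a patient who took only the wrong drug, the literal rule may omit the events instead.
- That each such patient moves both arms' rates by half a point. The 0.53 points is a ceiling. On the illustrative risks, one patient changes the expected difference from 8.0 to 7.96.

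**Conclusion.** The point holds as a low-priority design weakness. Followed as written, the safety rule misattributes events that arise on the wrong drug, and it leaves unclear whether a patient who took only the wrong drug is in the set at all.

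The size depends entirely on dispensing errors, for which the documents give no rate. With no errors the tables do not change, and with a handful the loss is a fraction of a percentage point for common events. The remaining reason to act is a rare event, where one case in the wrong column, or missing, could alter the reading. These sizes assume 190 patients per arm and, for the dilution formula, that affected patients took the other drug throughout.

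**What to change.** 1. In SAP 6.3.4 and Protocol 12.3.4, define the Safety Analysis Set as all randomized patients who took at least one dose of either double-blind study medication. Changing the grouping alone would not be enough, because the present membership rule could still exclude a patient who took only the wrong drug.
2. Group each patient once, by treatment actually received, with one prespecified rule for patients who took both drugs. One example is to use randomized treatment unless only the other drug was taken. Do not split a patient's events between arms: the SAP 10.1 tables are patient incidences by arm, and splitting would put one patient in two columns with no matching denominator.
3. List every patient whose received and randomized treatments differ, with dates and events. Under the example rule, events on the wrong drug in a mixed-exposure patient stay in the randomized column, so the listing is what makes them visible.
4. Bring Protocol 12.8 and the synopsis into line. Keep efficacy as randomized.

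The cost is one derived variable and one listing. The medication identification numbers and the dispensing records already required (Protocol 8.2.1 and 13.4.6) supply the data. The downside is a slight departure from the randomized comparison if any mismatch occurs.

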#### **6.3.5. Pharmacokinetic Analysis Set**

The PK Analysis Set includes all patients who have received at least 1 dose of study medication and have at least 1 confirmed, fasted, and analyzable sample. Patients must have been fasting for approximately 8 hours before the visit and must not have had any major protocol deviations that potentially affect exposure levels. The PK Analysis Set will be used for PK analyses.

#### **6.3.6. OLE Full Analysis Set**

The OLE Full Analysis Set (OLEFAS) includes all patients who have received at least 1 dose of study medication in the OLE. All efficacy and safety analyses during the OLE will be based on the OLE FAS. For the purposes of the analyses outlined in this SAP, patients will be analyzed according to randomized treatment assignment in the double-blind period.

### **6.4. Baseline Definition**

#### **6.4.1. Double-Blind Baseline**

Double-blind baseline is defined as the last nonmissing assessment prior to and including the first administration of study medication (including unscheduled assessments) in the study. In the case where the last nonmissing assessment and the study medication start date (and time if available) coincide, that assessment will be considered baseline. Unless explicitly stated, all baseline used in this SAP will refer to the double-blind baseline.

#### **6.4.2. Open-Label Extension Period Baseline**

OLE baseline is defined as the last nonmissing assessment prior to and including the first administration of sparsentan (including unscheduled assessments) in the open-label extension. In the case where the last nonmissing assessment and the sparsentan start date (and time if available) coincide that assessment will be considered baseline.

### **6.5. Derived and Transformed Data**

#### **6.5.1. Baseline Age**

Age is captured in the electronic data capture system as relative to the date of informed consent.

#### **6.5.2. Study Day**

Study day 1 is defined as the day on which the first dose of study medication is administered (Day 1/Week 0). All other study days will be calculated relative to that date. The day before the start of study medication is Day -1 (there is no Day 0).

Study day will be calculated using the following formula:

- study day = date – first dose date + 1, where date  $\geq$  first dose date

- study day = date – first dose date, where date < first dose date

### 6.5.3. Standard Calculations

Variables requiring calculation will be derived using the following formulas:

- Days – A duration expressed in days between 1 date (*date1*) and another later date (*date2*) will be calculated using the following formulas:  
duration in days = date2 – date1 + 1
- Months – A duration expressed in months is calculated as the number of days divided by 365.25/12 (approximately 30.4)
- Years – A duration expressed in years is calculated as the number of days divided by 365.25
- Height – Height entries made in inches (in) are converted to centimeters (cm) using the following formula:  
height (cm) = height (in) × 2.54
- Weight – Weight entries made in pounds (lb) are converted to kilograms (kg) using the following formula:  
weight (kg) = weight (lb) / 2.2046
- Temperature – Temperature entries in degrees Fahrenheit are converted to degrees Celsius using the following formula:  
temp (degrees Celsius) = 5 / 9 × (temp [degrees Fahrenheit] – 32)
- Change from baseline – Change from baseline will be calculated as:  
Change = post baseline value – baseline value
- Percentage change from baseline – Change from baseline will be calculated as:  
Percentage change from baseline = ([post baseline value – baseline value] / baseline value) × 100
- Percent change from baseline of variables analyzed in natural log will be calculated as:  
Percent Change = [exp (change in natural log) – 1] × 100

For variables requiring log transformation, natural log will be used.

### 6.5.4. Visit Windows

A visit window method will be applied to determine analysis visits across the study for efficacy and safety endpoints based on laboratory results, including eGFR and quantitative urinalysis (including UP/C). If a patient has multiple assessments (including unscheduled visits) within a visit window, the value closest to the target day for that visit will be selected for analysis. If more than 1 assessment is equidistant to the target day, then latest value will be selected. For efficacy analysis visits on or prior to Week 110, only assessments while the patient is on randomized treatment should be included (see [Section 8.1](#) for definition of on treatment).

The visit windows for the double-blind period shown in [Table 1](#) are defined for endpoints based on laboratory results. Visit windows for the OLE will be defined in a separate SAP.

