### 6.3.2. Permanent Discontinuation of Study Medication

During the course of this long-term study, it is anticipated that patients may permanently discontinue study medication for any of the following reasons:

- Receipt of a kidney transplant or initiation of chronic dialysis
- Any SAE, AE of interest (AEOI; see Section 10.3), clinically significant laboratory abnormality, intercurrent illness or other medical condition that indicates to the Investigator that continuation on study medication is not in the best interest of the patient
- Significant protocol deviation (ie, patient failed to meet entry criteria or did not comply with protocol requirements resulting in an unacceptable risk to the patient's health)
- Investigator discretion
- Patient decision to discontinue study medication
- Patient pregnancy
- Diagnosis of Class II-IV CHF
- Hyperkalemia resistant to treatment (see Appendix B, Section 15.2.2 for hyperkalemia management guidelines)
- Termination of the study by the Sponsor, Food and Drug Administration (FDA), or other regulatory authorities (see Section 13.4.5)
- Lost to follow-up

Receipt of systemic corticosteroid and/or immunotherapy intervention during the study is not a reason for permanent study medication discontinuation.

Patients who permanently discontinue study medication during the double-blind period should be encouraged to continue study visits through Week 114 for continued collection of safety and efficacy data despite stopping study medication but may withdraw consent at any time (see Section 6.5). Patients who agree to continue regularly scheduled study visits will complete the EOT assessments listed in the Schedules of Study Events (Section 15.1) as close as possible to the patient's last dose of study medication. Alternatively, if the last dose of study medication is on a scheduled study visit (eg, Week 58), that visit will be considered an EOT/ET visit, and EOT assessments will be performed. If an EOT/ET visit is completed in the double-blind period, study medication cannot be resumed. The visit data, including the primary reason for discontinuation

of study medication, will be recorded on the EOT eCRF. Subsequent study visit data will be recorded on the visit-specific eCRF.

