**Table 15.1-2. Double-blind Period: Schedules of Study Events from Week 48 Through End of Double-blind Period**

	Blinded Treatment Period							End-of-Blinded Treatment Period
Week	Week 48	Week 58	Week 70	Week 82	Week 94	Week 106	Week 110/EOT/ET a	Week 114
Visit	9	10	11	12	13	14	15	16
Visit Window	± 14 days	± 14 days	± 14 days	± 14 days	± 14 days	± 14 days	± 14 days	- 7/ + 14 days
Full Physical Examination		X					X	
Targeted Physical Examination	X		X	X	X	X		X
Peripheral Edema Assessment b	X	X	X	X	X	X	X	X
Vital Signs c	X	X	X	X	X	X	X	X
Clinical Laboratory Assessments Panel A d	X	X	X	X	X	X	X	X
Lipid Panel e	X	X	X	X	X	X	X	X
NT-proBNP	X	X	X	X	X	X	X	X
Aldosterone, Renin, Endothelin	X		X		X		X	X
Biorepository Samples (blood and urine, if consented)		X		X			X	X
Coagulation Tests (Prothrombin Time, INR)	X		X				X	
Quantitative Urinalysis (24-hour collection) f	X	X	X	X	X	X	X	X
Calculate eGFR g	X	X	X	X	X	X	X	X
PK Plasma Levels h	X		X		X		X	
Pregnancy Test i	X	X	X	X	X	X	X	X
QoL Questionnaires j	X		X		X		X	
Dispense Urine Pregnancy Tests k	X	X	X	X	X	X	X	
Informed Consent for OLE l							X	X
Study Medication Dispensing m	X	X	X	X	X	X		
Study Medication Accountability	X	X	X	X	X	X	X	
Adverse Event Assessment	-----Continuous Monitoring -----							
Concomitant Medications/Therapies	-----3 Months prior to screening followed by Continuous Monitoring -----							

Abbreviations: ALP = alkaline phosphatase; ALT = alanine aminotransferase; AST = aspartate aminotransferase; BUN = blood urea nitrogen; CKD-EPI = Chronic Kidney Disease Epidemiology; eCRF = electronic case report form; eGFR = estimated glomerular filtration rate; EOT = End-of-Treatment; EQ-5D-5L = EuroQol 5-dimension, 5-level QoL Questionnaire; ET = Early Termination; HDL = high-density lipoprotein; INR = international normalized ratio; KDQoL-36 = Kidney Disease QoL Questionnaire; LDL = low-density lipoprotein; MCH = mean corpuscular hemoglobin; MCHC = mean corpuscular hemoglobin concentration; MCV = mean corpuscular volume; NT-proBNP = N-terminal prohormone of brain natriuretic peptide; OLE = Open-label Extension; PK = pharmacokinetics; QoL = Quality of life; SF-12 = 12-Item Short Form Health Survey (QoL questionnaire); WBC = white blood cell; WOCBP = women of childbearing potential.

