**Table 1: Visit Windows (Study Days)**

Analysis Visit	Relative Target Day	Analysis Visit Window (Study Days)	
		eGFR and Safety Labs	Quantitative Urinalysis
Week 2	15	2 – 22	N/A
Week 4	29	23 – 36	2 – 36
Week 6	43	37 – 64	37 – 64
Week 12	85	65 – 127	65 – 127
Week 24	169	128 – 211	128 – 211
Week 36	253	212 – 295	212 – 295
Week 48	337	296 – 372	296 – 372
Week 58	407	373 – 449	373 – 449
Week 70	491	450 – 533	450 – 533
Week 82	575	534 – 617	534 – 617
Week 94	659	618 – 701	618 – 701
Week 106	743	702 – 757	702 – 757
Week 110 	771	758 – 785	758 – 785
Week 114 	799	>785	>785
4-week After EOT 	799  or Last Dose Date + 28 	>785  or >Last Dose Date 	>785  or >Last Dose Date 

eGFR = estimated glomerular filtration rate; EOT = end of treatment.

 For patients who completed the planned randomized treatment period.

 Efficacy endpoints only.

 For patients who discontinued the randomized treatment early.

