### **8.6.3. Sensitivity Analyses of the Key Secondary Efficacy Results**

Robustness of the key secondary efficacy endpoints due to missing data or premature treatment discontinuations (including the impact of COVID-19) will be explored by the following sensitivity analyses:

- Tipping point approach of the MI analysis as described in [Section 6.6.1.2](#)
- Mixed model random coefficients analysis using observed data (with no imputation of missing data)
- Mixed model random coefficients analysis using completers only (patients who completed treatment through 1-year and 2-year blind treatment period)
- Mixed model random coefficients analysis including local laboratory data with central laboratory data
- Mixed model random coefficients using observed data (with no imputation of missing data) during the double-blind period including after premature treatment discontinuation (treatment policy estimand). Additional analysis exploring potential intercurrent events that could impact the primary analysis (eg, premature discontinuation of study drug, use of immunosuppressive agents, loss to follow-up, withdrawal of consent, need for RRT, or death) may be performed to examine their impact.

To assess the impact of changes in immunosuppressive medications, the key secondary efficacy analysis will be repeated by excluding assessments after initiation of renal indication of systemic immunosuppressive medication in the blinded treatment period.

To assess the potential impact of patient evaluability and major protocol deviations, the key secondary efficacy analysis will be repeated using the PP Analysis Set.

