### **8.7.3. Other Continuous Endpoints**

The following exploratory endpoints will be analyzed using an MMRM as described for the primary efficacy endpoint ([Section 8.5.1](#)). Missing data will not be imputed using the MI procedure:

- The mean change from baseline in eGFR and selected proteinuria variables, based on a 24-hour urine sample (eg, urine protein excretion, urine albumin excretion, UA/C, and UP/C), up to Week 110
- Mean changes from baseline in QoL, measured via PRO at each visit
- Change from baseline for blood pressure will also be analyzed at both primary analysis and at final analysis.

The following exploratory endpoints will be analyzed using an ANCOVA analysis:

- The change from baseline in eGFR at 6 weeks post randomization (ie, the acute effect of randomized therapy)
- The change from EOT (ie, Week 110) in eGFR 4 weeks following cessation of treatment (ie, at Week 114)
- Duration of hospitalizations (for any reason and for reasons related to the kidney)

Specifically, the change from baseline or EOT or duration (as applicable) will be the dependent variable, treatment group, and randomization stratification strata as fixed effects and baseline value as covariate. The treatment effect will be the contrast between sparsentan and irbesartan LS means. The LS means, treatment effect estimate, 95% CI, and p-value will be presented.

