Specifically, the model will include treatment, time (ie, nominal visit in weeks), treatment by time interaction, and stratification strata factors as fixed effects, and patient as a random effect. A logit link function will be used with distribution set to binomial. An unstructured covariance matrix will be assumed; if convergence issues arise, a first order autoregressive structure will be used. Treatment effect estimates will be extracted from the model at each visit in terms of the difference between treatments in log odds, together with the associated 95% CI and 2-sided p-values. Treatment effects and CIs will be back transformed to provide results on the odds ratio scale.

At the primary analysis, analysis models without stratification by randomization strata or other simpler models may be used if sparsity of data causes model convergence issues.

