### 10.5. Vital Signs

The results and change from baseline to each post-baseline scheduled visits will be summarized for blood pressure (systolic and diastolic), heart rate, respiration rate, temperature, and weight.

The number and percentage of patients meeting the following criteria at any time during the study will also be summarized:

- Systolic blood pressure:
  - $\leq 100$  mmHg
  - A decrease from baseline more than 30 mmHg
  - $>180$  mmHg
  - An increase from baseline more than 40 mmHg
- Diastolic blood pressure:
  - $\leq 60$  mmHg
  - A decrease from baseline more than 20 mmHg
  - $>105$  mmHg
  - An increase from baseline more than 20 mmHg
- Heart rate:
  - $<45$  beats per minute
  - A decrease from baseline more than 20 beats per minute
  - $>120$  beats per minute
  - An increase from baseline more than 20 beats per minute

For the analysis of orthostatic hypotension, the number and percentage of patients with >20 mmHg decrease in systolic blood pressure at any time and the number and percentage of patients with > 10 mmHg decrease in diastolic blood pressure at any time will be presented.

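### SAP Table 1 closes the Week 110 window to patients who stop treatment early, so the treatment-policy sensitivity analyses and by-visit safety laboratory tables have no Week 110 value for them

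*SAP*

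**What the plan says.** - SAP 6.5.4 assigns laboratory results to analysis visits by study day: "A visit window method will be applied to determine analysis visits across the study for efficacy and safety endpoints based on laboratory results". Within a window the value closest to the target day is used, and the later one if tied. For efficacy visits up to Week 110 it admits on-treatment assessments only, which SAP 8.1 defines as up to 3 days after the last dose.
- In SAP Table 1 the Week 110 row (target Day 771, Days 758-785) and the Week 114 row (after Day 785) carry footnote 1: "For patients who completed the planned randomized treatment period". The rows from Week 2 to Week 106 carry no footnote.
- Early stoppers have one further row, 4-week After EOT. It targets last dose + 28 days, has no upper limit, and applies to efficacy endpoints only.
- The slope models in SAP 8.6.1 and 8.6.2 use analysis visit in weeks as time. SAP 8.6.3 adds a slope analysis of observed data "during the double-blind period including after premature treatment discontinuation (treatment policy estimand", and SAP 8.5.2 adds the matching MMRM for UP/C. SAP 5.4 says these followed regulatory advice.
- SAP section 10 bases safety analyses on on-study data, and 10.4 summarises laboratory results at each scheduled visit.
- Protocol 6.3.2 encourages patients who stop drug to continue visits through Week 114, so off-drug Week 110 values should exist.

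**The concern.** The treatment-policy analyses are there to show what happens when off-drug follow-up is kept. Under Table 1 an early stopper's off-drug value on Day 743 has a Week 106 slot, but the Day 771 value four weeks later has no Week 110 slot, and no reason is given. Because the slope model takes time from the analysis visit, a value without one cannot enter. Week 110 is the latest point in the slope and so carries high leverage, and the patients who lose it are those the analysis was added for. The Week 110 safety laboratory tables would likewise describe treatment completers only, although the section says they are on-study.

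**Working it through.** **1. The window itself.** Target day = 7 × week + 1, and limits are midpoints between neighbouring targets. For Week 110 the target is 7 × 110 + 1 = 771. The midpoint with Week 106 (743) is 757, so the window opens on Day 758. The midpoint with Week 114 (799) is 785. This reproduces 758-785, and the other twelve windows from Week 2 to Week 106 also reproduce. The days are right; the issue is who may use them.

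**2. Does the 4-week After EOT row rescue the value?** Take a patient seen on every target day and apply the closest-to-target rule:

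| Stop (week) | Last dose day | Target (+28) | Day selected |
|---|---|---|---|
| 58 | 407 | 435 | 491 (Week 70) |
| 94 | 659 | 687 | 743 (Week 106) |
| 102 | 715 | 743 | 743 (Week 106) |
| 104 | 729 | 757 | 771 (tie with 743, later taken) |
| 106 | 743 | 771 | 771 |
| 107 | 750 | 778 | 771 |
| 108 | 757 | 785 | 799 (tie with 771, later taken) |
| 109 | 764 | 792 | 799 |

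Day 771 is selected only for stops at about Weeks 104-107, and then as the post-EOT visit rather than Week 110. For safety laboratories the row does not apply at all.

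**3. Which analyses are touched.** The main eGFR and UP/C analyses exclude off-drug values by the on-treatment rule and impute them (SAP 6.6.1.1), so the footnote changes nothing there. The one possible exception is a patient classed as an early stopper with a last dose on Day 755 or later (755 + 3 = 758). The 1-year slope ends at Week 58 and is not involved. The UP/C contrast is at Week 36, so the treatment-policy MMRM is affected only indirectly, through the covariance between visits. The direct effect is on the 2-year treatment-policy slopes and the Week 110 safety laboratory tables.

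**4. Size for one patient.** Sum of squared deviations of visit times, in weeks²:
- Total slope, Weeks 2-110: 18,836 with Week 110 and 14,956 without, a loss of 20.6%.
- Chronic slope, Weeks 6-110: 13,578 with and 10,686 without, a loss of 21.3%.

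Per-patient variance of the annualised slope = 5.8² × 52.18² / Sxx + (slope SD)². The residual 5.8 is from the sample size section, 52.18 is weeks per year (365.25/7), and the slope SD is assumed to be 3 to 5 mL/min/1.73 m² per year because the documents give none. Information lost = 1 - (variance with / variance without).

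| Slope | Assumed SD | Variance with | Variance without | Information lost |
|---|---|---|---|---|
| Total | 3 | 4.86 + 9 = 13.86 | 6.12 + 9 = 15.12 | 8.3% |
| Total | 5 | 4.86 + 25 = 29.86 | 6.12 + 25 = 31.12 | 4.1% |
| Chronic | 3 | 6.75 + 9 = 15.75 | 8.57 + 9 = 17.57 | 10.4% |
| Chronic | 5 | 6.75 + 25 = 31.75 | 8.57 + 25 = 33.57 | 5.4% |

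**5. Size for the trial.** If 10-20% stop early and otherwise attend every visit (assumed), that is 38-76 of 380 patients. The loss runs from 0.10 × 4.1% = 0.4% to 0.20 × 10.4% = 2.1% of total slope information. The standard error widens by 1/√(1 - 0.004) - 1 = 0.2% to 1/√(1 - 0.021) - 1 = 1.1%.

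**The case against.** The strongest reply is that little depends on this. No primary or key secondary test is touched, Week 106 stays open to stoppers so their follow-up shortens by only four weeks, and SAP 8.6.3 plainly intends to use off-drug data. Safety laboratory shift tables to worst and last value (SAP 10.4.1, 10.4.2) do not depend on the Week 110 label. All of that stands, and it limits the size. It does not remove the contradiction between that intent and a table that gives the value no visit. It is also fair that the value is not shut out of every row, since the post-EOT window formally admits it; step 2 shows how rarely it is selected.

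A reader might infer something stronger: that blood pressure or quality-of-life readings taken at an early stop are analysed as Week 110, because the protocol schedule has one column headed "Week 110/EOT/ET", and because of a stop at a scheduled visit Protocol 6.3.2 says "that visit will be considered an EOT/ET visit, and EOT assessments will be performed". The documents do not support this. The column lists assessments and is not an analysis rule. The same protocol section puts early end-of-treatment data on the EOT eCRF and later visits on visit-specific eCRFs, so the records can be told apart. Nothing says that a visit at which drug is stopped loses its own week.

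What remains is missing detail. SAP 8.7.3 says "Change from baseline for blood pressure will also be analyzed at both primary analysis and at final analysis" and, like the quality-of-life analysis, uses the primary MMRM, whose time term is the analysis visit; none is defined for either measure. SAP 10.5 is no more specific: "The results and change from baseline to each post-baseline scheduled visits will be summarized for blood pressure". Hematuria differs: it is a urinalysis result, so the laboratory windows already cover it, but its model in SAP 8.7.4 uses "time (ie, nominal visit in weeks", which conflicts with 6.5.4.

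**Conclusion.** The point holds, and it is minor. Footnote 1 leaves early stoppers without a Week 110 analysis visit in the treatment-policy analyses and in the by-visit on-study safety laboratory summaries, with no stated reason. For the 2-year treatment-policy slopes the cost is 4-10% of an affected patient's slope information, or about 0.4-2% overall. Those figures rest on an assumed slope SD of 3-5 and an assumed 10-20% early stopping.

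Two wider inferences should not be drawn. The main slope analyses do not lose data through a window error, since they leave out off-drug values by design. And for blood pressure and quality of life the visit mapping is undefined rather than wrong, so no bias in those tables can be claimed from the text.

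**What to change.** 1. In SAP Table 1, delete footnote 1 from the Week 110 row. Keep it on Week 114, which represents four weeks after the planned end of treatment and has its own counterpart for early stoppers. The main analyses stay protected by the on-treatment rule; the deletion could add to them only on-treatment values that already fall in Days 758-785.
2. In SAP 6.5.4, state that the on-treatment restriction does not apply to the treatment-policy analyses of 8.5.2 and 8.6.3. Read literally, it now excludes the data they call for.
3. As a secondary clarification, map blood pressure, weight, edema and quality-of-life readings, including early EOT/ET records, to analysis visits by study day. Follow each endpoint's own schedule, since quality of life is collected at fewer visits. Reconcile nominal visit in the hematuria model (8.7.4) with the laboratory windows.

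The cost is a few sentences of SAP text and the existing window rule applied to more data sets, settled before unblinding. It needs no new data and does not affect patients.
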